1 LIST OF ABBREVIATIONS AND DEFINITIONS

Abbreviations	Definition
AA	Alcoholics Anonymous
AE	Adverse Event
AMPA	α -amino-3-hydroxy-5-methyl-4-isoxazolepropionic acid
APA	American Psychiatric Association
AUD	Alcohol Use Disorder
AUDIT	Alcohol Use Disorders Identification Test
BAC	Breath Alcohol Content
BBCET	Brief Behavioral Compliance Enhancement Treatment
BUN	Blood Urea Nitrogen
CBC	Complete blood count
CES-D	The Center for Epidemiologic Studies Depression Scale
CO	Carbon Monoxide
CIWA-AR	Clinical Institute Withdrawal Assessment for Alcohol-revised
CMDA	Cortico-mesolimbic dopamine
CNS	Central Nervous System
DDD	Drinks per drinking day
DrInC	Drinker Inventory of Consequences
DSMB	Data and Safety Monitoring Board
DSM-4	Diagnostic and Statistical Manual of Mental Disorders-4
DSM-5	Diagnostic and Statistical Manual of Mental Disorders-5
ECG	Electrocardiogram
ET	Early Termination
FDA	Food and Drug Administration
FTND	Fagerström Test for Nicotine Dependence
GABA	γ -aminobutyric acid-A
GGT	γ -glutamyl transferase
Heavy Drinking	5 or more drinks per drinking day for men, 4 or more drinks per drinking day for women
ID	Identification
IND	Investigational New Drug
IRB	Institutional Review Board
ITT	Intention-to-Treat
LDH	Lactate Dehydrogenase
MD	Medical Doctor
MINI	Mini International Neuropsychiatric Interview
MOS - Sleep	Medical Outcomes Sleep Scale
NIAAA	National Institute on Alcohol Abuse and Alcoholism
NIH	National Institutes of Health
NIMH	National Institute of Mental Health
NP	Nurse Practitioner
PANAS	Positive Affect Negative Affect Schedule
PDA	Percentage of Days Abstinent
PHDD	Percentage of heavy drinking days
PI	Principal Investigator

Abbreviations	Definition
PK	Pharmacokinetics
Q-LES-Q	Quality of Life Enjoyment and Satisfaction Questionnaire
SAE	Serious Adverse Event
SDU	Standard Drink Units
SGOT	Serum glutamic oxaloacetic transaminase
SGPT	serum glutamic pyruvic transaminase
SOP	Standard Operating Procedure
TARG	Tobacco and Alcohol Research Group
TLFB	Timeline Followback
TQD	Target Quit Date
UVa CLEAR	University of Virginia Center for Leading Edge Addiction Research
ULN	Upper Limit Of Normal
VTA	Ventral tagmental area
WSWS	Wisconsin Smoking Withdrawal Scale

2 STUDY SCHEMA

3 STUDY SCHEDULE

Randomization		Target Quit Date						
	Screen	Weeks 1 to 5 (-5 to -1 weeks to TQD)		Weeks 6 to 10 (0 to +4 weeks from TQD)	Weeks 10 to 18 (+4 to +12 weeks from TQD)	Week 19 (+13 weeks from TQD)	Follow-Up Visit 1 month	Follow-Up Phone Call 3 months
Assessments	X	Weekly	Week 6 visit=TQD (0)	Weekly	Biweekly	X	X	X
Psychosocial Intervention	—	Weekly		Weekly	Biweekly	X	—	—
Medication Dispensation	—	Weekly		Weekly	Biweekly	—	—	—

Table 1: Time and Events Schedule

Assessment		Investigational Product Administration																
Study Week	-4 to -1	1	2	3	4	5	6	7	8	9	10	12	14	16	18	19/ ET	F/U 1 month	F/U 3 month (phone)
Visit Number	S	1	2	3	4	5	6	7	8	9	10	11	12	13	14	15	16	17
Subject characteristics																		
Informed consent	x																	
Demographics	x																	
Alcohol Use Disorders Identification Test (AUDIT)	x																	
Fagerström Test for Nicotine Dependence	x															x	x	
Tobacco Use History Questionnaire	x																	
Baseline Drug Use	x																	
MINI for DSM-4, plus supplement	x																	
Efficacy																		
Timeline follow-back*	x	x	x	x	x	x	x	x	x	x	x	x	x	x	x	x	x	x
Carbon monoxide level	x	x	x	x	x	x	x	x	x	x	x	x	x	x	x	x	x	x
Urinary cotinine level****	x	x																
Quality of Life Enjoyment and Satisfaction Questionnaire (Q-LES-Q)	x	x	x	x	x	x	x	x	x	x	x	x	x	x	x	x	x	x
Alcohol Craving Visual Analog Scales	x	x	x	x	x	x	x	x	x	x	x	x	x	x	x	x	x	x
Nicotine Craving Visual Analog Scales	x	x	x	x	x	x	x	x	x	x	x	x	x	x	x	x	x	x
Salivary cotinine level	x															x		
Clinical Institute Withdrawal Assessment for Alcohol scale – Revised (CIWA-AR)	x	x	x	x	x	x	x	x	x	x	x	x	x	x	x	x	x	x
Wisconsin Smoking Withdrawal Scale	x	x	x	x	x	x	x	x	x	x	x	x	x	x	x	x	x	x
Positive Affect Negative Affect Schedule (PANAS)	x	x		x		x		x		x						x	x	
The Center for Epidemiologic Studies Depression Scale (CES-D)	x	x	x	x	x	x	x	x	x	x	x	x	x	x	x	x	x	x
Medical Outcomes Sleep Scale (MOS – Sleep)	x	x				x				x		x		x		x		
Drinker Inventory of Consequences (DrInC)	x	x			x		x		x	x	x	x	x	x	x	x		
Psychosocial intervention																		
Brief behavioral compliance enhancement treatment (BBCET)		x	x	x	x	x	x	x	x	x	x	x	x	x	x	x		

Assessment	Investigational Product Administration																	
	-2 to -1	1	2	3	4	5	6	7	8	9	10	12	14	16	18	19/ ET	F/U 1 month	F/U 3 month (phone)
Study Week																		
Visit Number	S	1	2	3	4	5	6	7	8	9	10	11	12	13	14	15	16	17
Subject characteristics																		
Clearing the Air Booklet	x																	
Compliance																		
Medication compliance measures	x	x	x	x	x	x	x	x	x	x	x	x	x	x	x	x		
BBCET session checklist	x	x	x	x	x	x	x	x	x	x	x	x	x	x	x	x		
Genotyping	x																	
Study Drug Dispensing	x	x	x	x	x	x	x	x	x	x	x	x	x	x	x	x		
Safety																		
Other Drug Use	x	x	x	x	x	x	x	x	x	x	x	x	x	x	x	x	x	
Medical history	x																	
Physical exam**	x																x	
Vital signs (blood pressure, heart rate, weight)	x	x	x	x	x	x	x	x	x	x	x	x	x	x	x	x	x	
Electrocardiogram	x																x	
Breathalyzer (BAC)	x	x	x	x	x	x	x	x	x	x	x	x	x	x	x	x	x	x
Urine pregnancy test	x	x			x			x			x		x		x		x	
Concomitant medications	x	x	x	x	x	x	x	x	x	x	x	x	x	x	x	x	x	
Adverse events	x	x	x	x	x	x	x	x	x	x	x	x	x	x	x	x	x	
Blood chemistry	x																	x
Hematology	x																	x
Urine Drug Screen***	x							x							x		x	
Urinalysis	x																	
Contraceptive method	x	x	x	x	x	x	x	x	x	x	x	x	x	x	x	x	x	

Key:

S = screen is 30 days prior to visit #1 (weeks -4 to -1).

Randomization will occur before week 1 of double-blind treatment.

F/U = follow-up at months 1 and 3.

*Timeline follow-back will quantify both smoking and drinking behavior.

**Physical Exam may be done at screening or on or prior to visit 1.

***If positive at screen subject will be advised to stop using and will be allowed one repeat urine drug screen. Must provide negative results prior to randomization.

**** If subject registers a CO level of <10, a urinary cotinine will be administered. Subjects must have a cotinine level of ≥ 3 at Screen and prior to Randomization to be eligible for study inclusion.

4 ABSTRACT

Objectives

Primary: The primary objectives of this study are to assess the efficacy of both low- and high-dose topiramate in reducing the percentage of heavy drinking days (PHDD), while also increasing the continuous abstinence rate for smoking determined by a combination of self-report and carbon monoxide (CO) monitoring after the target quit date (TQD), and in the last 4 weeks of treatment. We propose that high-dose topiramate will be more efficacious than low-dose topiramate at reducing PHDD and increasing the continuous abstinence rate for smoking determined by a combination of self-report and CO monitoring after the TQD in the last 4 weeks of treatment after TQD.

Secondary: Secondary objectives include assessing that both low- and high-dose topiramate will be more efficacious than placebo at improving quality of life and reducing alcohol and nicotine craving in the last 4 weeks of treatment after TQD; high-dose topiramate will be more efficacious than low-dose topiramate at improving quality of life and reducing craving after the TQD, and in the last 4 weeks of treatment;

Exploratory: Improvements in quality of life and craving reductions will be predictably associated with reduced PHDD, increased continuous abstinence rates for smoking, or both, irrespective of treatment group.

Study Design: Two hundred and ninety-four comorbid alcohol- and nicotine-dependent subjects who meet eligibility criteria will be randomized to 1 of 3 treatment groups — placebo, low-dose topiramate (up to 125 mg/day), or high-dose topiramate (up to 250 mg/day). Randomization will be achieved using a block randomization procedure in which treatment groups will be stratified to achieve a balance on age of onset for alcoholism (less than 26 years old or 26 years and older), gender, and drinks per drinking day (DDD) (< 8 DDD or \geq 8 DDD) and the number of cigarettes smoked (<20 or \geq 20 cigarettes/day).

Following randomization, subjects will participate in an 18-week, double-blind treatment period during which they also will receive weekly Brief Behavioral Compliance Enhancement Treatment (BBCET) and a self-help manual for smoking cessation. Topiramate and matching placebo will be titrated for the first 5 weeks of the 18-week treatment period. The TQD will be at the beginning of the 6th week of treatment. Subjects will be instructed not to attempt smoking or alcohol cessation prior to the TQD. Setting a TQD at the end of medication titration enables stability of effects, comfort with the medication prior to attempting to cease alcohol and smoking consumption, and an appreciable buildup of medication.

Study Pre-Screening Procedures: Potential subjects will call a study phone number, which will be set up for each participating site. The intake interviewer will answer queries from the subject about the nature and demands of the study. The interviewer will request permission from the potential subject to collect data that will be part of the telephone screening interview. Confirmation of consent will be completed by the subject providing his or her name and telephone number. The telephone screening interview will include demographic data, physical

status, psychiatric history, timeline follow back (TLFB) for alcohol and cigarettes, and questions to assess motivation to engage in treatment. One such question to assess motivation will read as follows: “Are you willing to quit both smoking and drinking 30 – 60 days into the study?” Subjects who answer “yes” and meet all additional eligibility criteria will be preferably scheduled for a screening visit within 30 days of the telephone screening interview.

Study Screening Procedures: At the screening visit (visit S) subjects will be provided with information about the study, its rationale, risks, and potential benefits, and the role of the Institutional Review Board. All questions pertinent to the study raised by the potential subject will be answered before consent is signed. Those who complete all screening procedures and assessments and who are eligible for the study will be scheduled for a randomization visit (visit 1). Those who complete the screening procedures, but who are not eligible for study inclusion will be provided with the address and telephone number of another treatment center or will be referred to other research studies at the research site.

Study Duration: Each subject will remain in the study for 19 weeks including a follow up visit at 1 month and a follow up phone call at 3 months. The expected ratio of intake screens to enrolled subjects is approximately 2:1. Thus, the enrollment of 294 individuals will require 588 intake sessions over approximately 54 months of recruitment. Of the enrolled 294 individuals, the expected dropout rate is 30%; therefore, 206 individuals will be expected to complete all 18 weeks of double-blind treatment.

Sample Size: Two hundred and ninety four (294) subjects will be randomized to one of 3 groups, low-dose topiramate, high-dose topiramate or placebo control.

Population: Entry into this study is open to treatment seeking men and women at least 18 years of age and to all racial and ethnic subgroups. A Diagnostic and Statistical Manual of Mental \geq Disorders-5 (DSM-5) diagnosis of mild to severe alcohol use disorder is required and subjects must smoke an average of \geq 5 cigarettes/day in the 30 days prior to randomization.

Investigational Project: Subjects will be randomized on Study Day 1 to one of the following three groups:

1. Low-dose topiramate (up to 125 mg/day); or
2. High-dose topiramate (up to 250 mg/day); or
3. Identical matched placebo control.

To mask the intervention groups, identical matched placebo will be provided.

Dose titrations will be as follows:

The titration scheme has been devised such that this process is completed for the low- or high-dose topiramate groups, and matching placebo, at the end of week 5 (i.e., beginning of week 6). Both titration schemes are provided below.

Topiramate high-dose escalation schedule

Week	A.M. Dose	P.M. Dose	Total Daily Dose
1	-	50 mg	50 mg
2	50 mg	50 mg	100 mg
3	75 mg	75 mg	150 mg
4	100 mg	100 mg	200 mg
5	125 mg	125 mg	250 mg
6-18	125 mg	125 mg	250 mg

Topiramate low-dose escalation schedule

Week	A.M. Dose	P.M. Dose	Total Daily Dose
1	-	25 mg	25 mg
2	25 mg	25 mg	50 mg
3	37.5 mg	37.5 mg	75 mg
4	50 mg	50 mg	100 mg
5	62.5 mg	62.5 mg	125 mg
6-18	62.5 mg	62.5 mg	125 mg

Outcomes:

Primary Efficacy Outcomes: The timeline follow-back (TLFB) method of measuring alcohol and cigarette consumption will be used to construct a retrospective index of smoking behavior during the 3-month period before enrolling in the study. Thereafter, the consumption of alcohol or cigarettes between weekly visits will be recorded.[1] Days abstinent will refer to the number of days on which the subject consumes no alcohol or cigarettes. While subjects also will be provided with daily record cards as an aide-mémoire, only the TLFB data will be used in the efficacy analyses. From these data, we will determine both the PHDD and the point prevalence smoking abstinence rates. Self-reported reports of smoking cessation will be corroborated by measurement of breath CO level, and, when necessary, urinary cotinine level (see below). PHDD is calculated as days for which the number of drinks was five or greater for men and four or greater for women, divided by the number of study days. [73]

Expired carbon monoxide (CO) level will be measured using a Bedfont CO monitor, and, when necessary, Accutest NicAlert strips Self-reported abstinence will be verified by expired CO samples of <10 ppm. Individuals who report smoking at screen and visit 1, but register less than 10ppm on the CO monitor will be re-tested with a NicAlert cotinine strip. Urinary cotinine scores of 3 or higher indicate tobacco usage.

Secondary Efficacy Outcomes:

1. The Quality of Life Enjoyment and Satisfaction Questionnaire (Q-LES-Q)
2. The Alcohol Craving Visual Analog Scales
3. The Nicotine Craving Visual Analog Scales

Exploratory Outcomes:

Psychological Assessments:

1. Fagerström Test for Nicotine Dependence
2. Revised Clinical Institute Withdrawal Assessment for Alcohol scale (CIWA-Ar),[2]
3. Wisconsin Smoking Withdrawal Scale
4. Positive Affect Negative Affect Schedule (PANAS)
5. The Center for Epidemiologic Studies Depression Scale (CES-D)
6. Medical Outcomes Sleep Scale (MOS-Sleep)
7. The Drinker Inventory of Consequences (DrInC)[3]

Study Retention and Compliance:

1. Attendance at regularly scheduled clinic visits
2. We shall assess compliance by comparing unused capsule count to dispensing logs and dosing records (number of capsules dispensed, number of capsules expected to be taken, versus the number returned).
3. Brief behavioral compliance enhancement treatment (BBCET)

Safety Assessments:

1. Medical history
2. Physical examination
3. Vital signs

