12 INTERVENTIONS

12.1 Investigational Agents

Topiramate will be self administered by subjects in a dosing regimen of one capsule in the evening beginning on Day 1, Week 1 and then moving to one capsule in the morning and one capsule in the evening beginning on Day 8, Week 2 and continuing through Day 126, of Week 18.

The titration scheme has been devised such that this process is completed for the low- or high-dose topiramate groups, and matching placebo, at the end of week 5 (i.e., beginning of week 6). Both titration schemes are provided below:

Topiramate high-dose escalation schedule

Week	A.M. Dose	P.M. Dose	Total Daily Dose
1	-	50 mg	50 mg
2	50 mg	50 mg	100 mg
3	75 mg	75 mg	150 mg
4	100 mg	100 mg	200 mg

5	125 mg	125 mg	250 mg
6-18	125 mg	125 mg	250 mg

Topiramate low-dose escalation schedule

Week	A.M. Dose	P.M. Dose	Total Daily Dose
1	-	25 mg	25 mg
2	25 mg	25 mg	50 mg
3	37.5 mg	37.5 mg	75 mg
4	50 mg	50 mg	100 mg
5	62.5 mg	62.5 mg	125 mg
6-18	62.5 mg	62.5 mg	125 mg

Missed Doses. If a subject misses a week or more of investigational products, the product may be re-introduced with the A.M. dose for two days, then only the P.M. dose for the following two nights and by day 5 both doses should be taken, if tolerated. If a subject misses up to 6 consecutive days' doses, s/he will be instructed to start taking the investigational product at the last dose that s/he was taking before stopping. If the subject realizes he/she missed the AM dose and it is after 12pm then the subject should not take missed AM dose. A missed AM dose can be taken anytime before 12pm of the same day. If the subject realizes he/she missed the PM dose and it is the next day then the subject should not take missed PM dose. A missed PM dose can be taken before 24:00 (midnight) of the same day.

Medication Management. Pills may be taken with or without food. If a subject cannot tolerate a dose, the dose will be de-escalated to the next lower tolerated dose and a new kit will be ordered from Greenpark Compounding Pharmacy. Until the new kit arrives, subjects will take only one of their two daily pills. On an as needed basis and with the judgment of the site PI, both doses can be moved to the PM to manage sedation.

Placebo Control: Subjects assigned to the placebo group will receive the same number of matched placebo capsules on the same schedule as the topiramate high-dose and low-dose groups.

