15 ANALYTICAL PLAN

15.1 Outcome Measures

The primary efficacy variables will be the PHDD for the drinking outcome and the continuous abstinence rate for the smoking outcome (during the last 4 weeks of treatment, i.e., weeks 15–18 inclusive), respectively. The secondary efficacy variables will be quality of life and measures of alcohol and nicotine craving. Exploratory outcomes include measures of dependence, and measures of nicotine and alcohol withdrawal including negative effect, as noted below:

1. Fagerström Test for Nicotine Dependence
2. Revised Clinical Institute Withdrawal Assessment for Alcohol scale (CIWA-Ar) [2]
3. Wisconsin Smoking Withdrawal Scale
4. Positive Affect Negative Affect Schedule (PANAS)
5. The Center for Epidemiologic Studies Depression Scale (CES-D)
6. Medical Outcomes Sleep Scale (MOS-Sleep)
7. The Drinker Inventory of Consequences (DrInC)[3]

Additional exploratory outcome variables will include other: 1) measures of drinking severity (i.e., DDD) and abstinence (i.e., percentage of days abstinent; PDA) averaged across either the entire double-blind period or the last 4 weeks of treatment, and 2) smoking measures including the point prevalence abstinence rate and the CO level over either the entire double-blind period or the last 4 weeks of treatment.

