15.4 Subject Populations

The ITT population will be used for the primary analysis and is defined as the subjects who are randomized into the study. The evaluable population is defined as those subjects randomized to the study who completed at least 6 consecutive weeks of maintenance investigational product administration with a dose of at least 50 mg per day for at least 5 days of each 7-day weekly period. The safety population includes all subjects who received at least one dose of investigational product.

Analysis: Data will be summarized with respect to the primary and secondary outcome measures, demographics, and baseline characteristics. In general, quantitative variables will be summarized with standard descriptive statistics (e.g., range, quartiles, means, standard deviations), while frequency tables will summarize categorical variables. Group comparison for quantitative variables will be performed using standard two-sample t-tests or analysis of variance as appropriate. Highly skewed variables may be transformed prior to inferential comparison, or non-parametric methods may be used if needed. Group comparison for categorical variables will be analyzed with two-sample comparisons of proportions, or chi-square tests as appropriate.

The primary efficacy variables will be the PHDD for the drinking outcome and the continuous abstinence rate for the smoking outcome (during the last 4 weeks of treatment, i.e., weeks 15–18 inclusive), respectively. The secondary efficacy variables will be quality of life and measures of alcohol and nicotine craving.

Exploratory outcome variables will include other: 1) measures of drinking severity (i.e., DDD) and abstinence (i.e., percentage of days abstinent; PDA) averaged across either the entire double-blind period or the last 4 weeks of treatment, and 2) smoking measures including the point prevalence abstinence rate and the CO level over either the entire double-blind period or the last 4 weeks of treatment; 3) psychological assessments including measures of nicotine and alcohol withdrawal (WSWS, MOS-Sleep, CIWA-Ar), negative affect (PANAS, CES-D), dependence (FTND), drinking behavior (DrInC) and compliance (BBCET).

The general approach to statistical analyses will be the same as what we utilized in our previous studies.[4, 5] All randomized subjects will be included in the analysis using the intent-to-treat principle. Statistical analyses will be conducted using SAS 9.1 (SAS Institute Inc., Cary, NC).[6]

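### The PHDD denominator is undefined and no rule covers unobserved days, so with 30% expected dropout the drinking primary outcome is either distorted or missing for many randomised subjects

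*Combined protocol and SAP*

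**What the plan says.** The Abstract (section 4, Primary Efficacy Outcomes) gives the only formula for PHDD: days with five or more drinks for men and "four or greater for women, divided by the number of study days". It does not say whether study days are scheduled days, days enrolled, or days with TLFB data, and it names no time window.

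Section 15.1 supplies the window, "during the last 4 weeks of treatment, i.e., weeks 15–18 inclusive"; sections 6.1 and 15.4 agree. Section 15.4 states "The ITT population will be used for the primary analysis and is defined as the subjects who are randomized into the study" and later "All randomized subjects will be included in the analysis using the intent-to-treat principle".

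The Abstract (Study Duration) says "Of the enrolled 294 individuals, the expected dropout rate is 30" percent, so that "206 individuals will be expected to complete all 18 weeks of double-blind treatment".

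The primary model for PHDD, named in section 15.4 under Primary Outcomes Analytical Models, is a generalized linear model. The same passage adds that other repeated-measures approaches will be considered if attrition is differential. It names no trigger and chooses no method. Section 15.5 takes a different line: the drinking power calculation rests on a mixed model of weekly PHDD, and because that model already allowed for dropout, the plan says nothing further is needed for attrition.

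**The concern.** A ratio outcome needs a rule for days on which nothing was recorded. Here the numerator can be filled only from TLFB, the denominator is a term open to several readings, and the analysis must include people who may have left before the window opens. Two analysts could apply the text in good faith and obtain different values for the same subject.

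At stake is the size, and possibly the direction, of the treatment contrast on a primary outcome. The high-versus-low dose comparison is exposed in the same way as each comparison with placebo, because any of the three arms may lose people at a different rate.

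**Working it through.** **The plan's own figures.** 294 × (1 − 0.30) = 205.8, which rounds to the stated 206. That leaves 294 − 206 = 88 non-completers, about 29 per arm (88/3). The 98 per arm in section 15.5 also reproduces: 10% versus 28%, two-sided alpha 0.017, 80% power and no continuity correction give 98 (99 if alpha is taken as 0.05/3). That figure comes from smoking abstinence, so nothing below changes it.

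**The window.** Weeks 15–18 are 4 × 7 = 28 days of a treatment period "continuing through Day 126, of Week 18".

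**One subject with no TLFB data in the window.**
- Scheduled days as denominator, with absent days adding nothing to the numerator: 0/28 = 0%, the lowest possible value.
- Days enrolled or days with TLFB data as denominator: 0/0, no value.

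The reading also matters over the whole treatment period. Someone who leaves after 63 observed days, 32 of them heavy, scores 32/126 = 25% or 32/63 = 51%.

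**Arm means with scheduled days.** Let p be the true PHDD, taken as equal in leavers and stayers within an arm, and d the share of the arm with no data in the window. The arm mean becomes p × (1 − d). The documents give neither a PHDD level nor dropout by arm, so p = 30–70% and d = 20–40% are assumptions.

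- Equal dropout, d = 30%: means of 30, 50 and 70% become 21, 35 and 49%. A true difference of 10 points becomes 10 × 0.70 = 7.
- Unequal dropout, no true effect: false difference = (d_active − d_placebo) × p, in points:

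| Dropout, placebo / active | p = 30% | p = 50% | p = 70% |
|---|---|---|---|
| 30% / 30% | 0 | 0 | 0 |
| 25% / 35% | 3 | 5 | 7 |
| 20% / 40% | 6 | 10 | 14 |

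Positive values favour the active arm. If placebo loses more people, the sign reverses.

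**Why these are upper bounds for each split.** The table treats every dropout as gone before week 15. If leaving times were spread evenly over 126 days, the unobserved share of the window would be d × (98/126 + 0.5 × 28/126) = 0.889d. The 20%/40% case at p = 50% then gives 0.20 × 0.889 × 50 = 8.9 points instead of 10.

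**Observed days as denominator.** No day is falsely scored, but up to about 88 subjects have no weeks 15–18 value. A generalized linear model with one PHDD value per subject would drop them unless values are imputed, and no imputation is specified. The analysis would then no longer contain everyone randomised.

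**Sections 15.4 and 15.5 side by side.** The reassurance on attrition in 15.5 belongs to a mixed model of weekly PHDD. Section 15.4 does not name that model as primary; its two-part random-effects model of daily data is listed as exploratory. The reassurance therefore does not carry over to the primary analysis as written.

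**The case against.** A reader might infer that the plan scores anyone who leaves as having no heavy drinking, so that dropout passes for treatment success. The documents do not support that.

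- No section says that an unobserved day counts as non-heavy. Study days can equally mean days the subject was in the study. Since only TLFB data feed the efficacy analyses, absent TLFB arguably leaves the numerator unknown, not zero.
- The weekly mixed model in section 15.5 fits missing weeks being treated as missing. Section 15.4 also foresees informative dropout, if only loosely.
- Section 15.4 says the analysis follows the group's earlier trials, which may hold a day-level rule. Those sources are not available here, so the intended handling cannot be asserted either way.
- A false benefit for topiramate requires the topiramate arms to lose more people. With equal dropout the scheduled-day reading attenuates a true effect; with more loss on placebo it works against the drug.
- Not every non-completer lacks data. Subjects who stop medication may remain in the study (sections 12.2 and 13.10), missed visits can be done by telephone (13.4), and an early-termination visit is requested (13.6).

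All of this narrows the claim and makes the tabulated sizes upper bounds. It does not settle the denominator, supply a rule for the days that stay unobserved, or reconcile the primary model in 15.4 with the attrition argument in 15.5. The fallback in 15.4 applies only to differential attrition, whereas equal dropout also distorts the result under the scheduled-day reading.

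**Conclusion.** The gap is real and affects a primary outcome. The denominator is undefined, no rule covers unobserved days, and each available reading causes a problem under the plan's own 30% dropout.

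With scheduled days and missing days not counted as heavy, equal dropout before the window shrinks a true difference by 30%. Unequal dropout biases it by at most 3–7 points (25% versus 35%) or 6–14 points (20% versus 40%), in either direction. These sizes assume a true PHDD of 30–70% in dropouts and the dropout splits shown; neither is in the documents. With observed days, up to about 88 of 294 subjects have no value for the named primary model.

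The point is not that the plan already scores leavers as successes, nor that the bias must favour topiramate.

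**What to change.** 1. Define PHDD as heavy drinking days divided by days with TLFB data in the period concerned. State that days without TLFB data are missing and never counted as non-heavy.
2. Make the primary estimate the weeks 15–18 contrast from a likelihood-based repeated-measures model of weekly PHDD in all randomised subjects. This is the type of model on which section 15.5 relies. A new denominator alone is not enough, because subjects with no days in the window would still have no value. State also how a subject with no TLFB after randomisation enters the model.
3. Use TLFB from telephone visits and the 1- and 3-month contacts to recover days in the window where the recall reaches them. An early-termination TLFB can supply only days up to that visit.
4. Add a sensitivity analysis that counts missing days as heavy, or at the subject's baseline level, because the primary model assumes data are missing at random. Counting missing days as heavy is a severe bound: with 20% versus 40% dropout and a true PHDD of 50%, it moves the contrast by (0.40 − 0.20) × (100 − 50) = 10 points against the arm with more dropout.

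The cost is a change to the stated primary model, some added analysis, and an explicit missing-at-random assumption. The TLFB contacts are already scheduled, and the 98 per arm is unchanged.
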